A.3.1.5.1. Face-to-face interview or phone interviews at two weeks (Delirium group only): The purpose of this 10-15 minute face-to-face or phone interview is to repeat the delirium assessment to better assess the duration and persistence of the index delirium episode. This interview will be conducted at 2 weeks after hospital admission in patients who had delirium at any time during the index hospitalization. This interview will be conducted in all settings of care, including

hospital, home, assisted living, post-acute, or nursing home settings. We have extensive experience conducting interviews in all these settings, and the initial informed consent process will include these follow-up interviews. The two-week time period was selected for this interview, because previous work by our group has demonstrated the prognostic importance of the two week period: patients who resolve their delirium by 2 weeks regained their baseline functioning, whereas those with persistent delirium did not (Kiely 2006).

A.3.1.5.2. Retest face-to-face interviews at one and two months follow-up (Retest 1 and 2): The purpose of these 45 minute face-to-face interviews is to repeat our delirium assessments and neuro-psychological test battery to test for both the persistence of delirium and to evaluate retest (learning) effects. All subjects will be interviewed, although only a subset will have developed delirium while hospitalized. The Retest 1 interview (at 1 month) will assess for immediate learning or retest effects, particularly in the patients with normal cognitive functioning. The Retest 2 interview (at 2 months) will assess for delayed learning effects, which our preliminary results suggest are likely to be present in the delirious patients. Patients will also be asked about any rehospitalizations or intercurrent illnesses.

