A.3.2.3.1. Delirium presence: The presence of delirium will be rated by the dichotomous yes/no diagnosis of delirium based on the validated Confusion Assessment Method (CAM) algorithm. This 4-item algorithm will be used to make a diagnosis of delirium based on DSM criteria. It has excellent psychometric properties, and is widely used in both research and clinical settings. The CAM rating will be completed at baseline, daily during each hospitalization, and at each follow-up assessment, based on information from the interview, 3MS (baseline/every 6 mos) or other cognitive screen (daily in hospital), digit span testing, DSI, and MDAS. Delirium by interviewer rating (CAM criteria) will be augmented with delirium rated as present by medical record review during the index hospitalization, since delirium can occur between interviews. For this study, we are assuming a delirium rate of at least 25% for the surgical cohort. We are also assuming that the vast majority of delirium occurs (or at least begins) in the hospital setting; delirium is rare in community settings. The Delirium Symptom Interview (*Albert 1992*) will be used to rate delirium symptoms and is useful to help with the completion of the CAM rating. This is a brief instrument that includes both questions asked directly of the patient and a series of structured observations. It is used specifically to determine the presence or absence of eight key features of delirium, as originally defined by the DSM-III criteria. Use of this method in conjunction with the CAM has been previously described (*Simon 2006*). For hospitalizations during follow-up, a validated chart rating of delirium (*[name] 2005*) will be completed.

A.3.2.3.2. Delirium severity: Delirium severity will be rated with the widely-used Memorial Delirium Assessment Scale (*Breitbart 1997*), a 10-item scale that uses information from the MMSE and structured observations to rate delirium severity. Each item is rated as 0-3, to generate a 0-30 scale (30=most severe).

A.3.2.3.3. Delirium duration and recurrence: Delirium duration will be determined as the total number of delirium-days (as rated by a positive CAM rating) during hospitalization in the

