(baseline), 2) immediately after surgery in the post-anesthesia care unit (PACU), 3) on postoperative day 2 (POD 2), and 4) one-month after surgery. We will also collect a single baseline blood sample on 120 participants in a non-surgical comparison group. During the baseline assessment, three green top tubes (30 cc) will be collected. At all follow-up time points, two green top tubes (20 cc) will be collected. Blood samples will be collected via peripheral venipuncture or central venous line (if available in the PACU and on POD 2). Blood samples will be collected into sterile vacuum tubes using either a vacutainer or butterfly system, at the preference of the phlebotomist. Every attempt will be made to “piggyback” our blood collection on clinically scheduled blood draws. For participants being assessed at home, blood will be drawn by a trained member of our research team. All collected blood will be centrifuged to separate plasma from cellular products, divided into small samples, and frozen at -80C for future use.

A.4.2. Biomarker discovery methods

Using these samples, at the end of year 2 we will create a matched longitudinal biomarker discovery sample of 50 surgical participants with delirium and 50 matched surgical participants without delirium. In year 4 of our study we will create an independent biomarker validation sample of 100 surgical participants (50 with delirium and 50 matched controls without delirium). Using the biomarker discovery sample, we will describe a cytokine “signature” for delirium using the Luminex multiplex analyzer system that simultaneously measures 28 plasma cytokines. We will confirm this cytokine signature in the discovery sample and validate it in the biomarker validation sample using Enzyme – linked Immunosorbant Assays (ELISA). Similarly, using the biomarker discovery sample, we will use quantitative mass spectrometry proteomics to describe a plasma protein “signature” for delirium. We will perform two validations: first, using proteomics in the biomarker validation sample, and then using ELISA in the combined discovery and validation samples. Using the combined biomarker discovery and validation samples, we will examine the relationship of the cytokine and protein signatures for delirium with cognitive and functional outcomes up to 18 months after non-cardiac surgery.

A.4.3. Measurement of the Apo E allele

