B.1.1.3 Sample Size for Project 1 Validation study: Our goal is to enroll 50 patients over 2 years from the SAGES study cohort who are in the follow-up phase. Validation testing will occur once.

B.1.1.4 Sample Size for Project 1 Pain-Delirium sub-study: Our goal is to include all surgical patients from the SAGES study cohort. All patients provided written consent to review their medical charts.

B.1.2. Sample Size for Project 2. For Project 2 (biomarkers study), we will use principal component analysis to examine the relationship of biomarkers to delirium at each of the four time points in the biomarker discovery sample (N=100). Due to lack of information on the distribution of cytokine principal components, we computed power based on a fraction of the standard deviation. We used PROC POWER from SAS/STAT software. The power estimate is based on the 2-tailed 2-sample t-test for testing a difference between the absolute difference of the mean level of the biomarker principal component between those with and without delirium with Type-I error set at 0.05. The other factor that influences power is the degree of correlation of biomarker levels within matched pairs relative to the overall sample. This represents the ability of the matching procedure to remove “noise” with regard to confounders and focus the analysis on the key variable: the presence or absence of delirium. We performed the power analysis with a worst case scenario (no correlation), and best case scenario (moderate correlation, Pearson $r=0.3$). Our power calculations demonstrate that we can detect 0.57 S.D. unit differences (medium effect) under the worst case scenario and a 0.26 SD unit (small effect) differences under the best case scenario between delirium and non-delirium groups with 80% power. These are small to medium effect sizes and well below the differences in biomarkers seen in our pilot data. Therefore, we have good to excellent power for our biomarker discovery aims.

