Nicotinamide adenine dinucleotide (NAD) function: The [name] lab will explore differences in oxidative functioning particularly in relationship to NAD function. The [name] lab (BIDMC) will assess inflammatory markers.

Generation of iPSCs: The HSCI iPSC Core Facility will derive and characterize iPSC lines on a fee-for-service basis. The iPSC Core has extensive experience in iPSC derivation from human blood using all current methods of reprogramming. The Core offers both derivation and characterization services so that the appropriate quality control measures can be put in place to ensure quality iPSC lines. The [name] and [name] labs will maintain the primary iPSC lines. The intent will be to eventually deposit these iPSC lines in a biorepository that has experience with banking and distributing human pluripotent stem cells. These labs have considerable experience in the manipulation and analysis of iPSC lines. We anticipate that these iPSC lines will be a valuable resource not only for this study but for the aging research community at large.

Table 3. Overview of Project Hypotheses and Analytic Approaches.

Project	Aim or Hypothesis	Outcome(s)	Predictor(s)	Approach(es)	NSC	Effect of Interest
1	Aim 1-2	Cognitive decline	Delirium Delirium Severity	GLMM	*	Time by delirium interaction
	Aim 3	Functional decline and health care utilization	Delirium	GLMM	*	Time by delirium interaction
2	Aim 1	Delirium	Cytokine signature	PCA, CLR		Cytokine profile dif. by delirium
	Aim 2	Delirium	Protein signature	SVM, PCA, CLR		Protein profile dif. by delirium
	Aim 3	Cognitive, functional decline	Cytokine/Protein signature Fractional CSF	GLMM	o	Reg. of change on predictor
3	H 1.1	Delirium incidence	volume	GLM		Reg. of outcome on predictor
	H 1.2	Delirium incidence	WMH volume	GLM		Reg. of outcome on predictor
	H 1.3	Delirium incidence	Global blood flow	GLM		Reg. of outcome on predictor
	H 2.1-3	Change in neuroimaging marker [‡]	Delirium	GLMM		Reg. of outcome on predictor
	H 3.1-2	Neuroimaging marker [‡]	GCP Biomarker signature	GLM		Reg. of outcome on predictor
	H 3.3	Delirium incidence, Cognitive decline	Neuroimaging marker x Cognitive Reserve [†]	GLMM	o	Effect modification of neuroimaging marker [‡] x Cognitive reserve [†]
4	Aim 2, H 1	Delirium incidence Cognitive, Functional	Reserve [†]	GLM, DTS	*	Reg. of outcome on predictor
	Aim 3, H 2-3	decline	Reserve [†]	GLMM, LGC		Reg. of outcome on predictor

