C.1.2. Exclusionary criteria are: (1) Probable dementia, other than mild impairment (by 3MS): we will implement a two-stage process to exclude all patients with probable dementia, mild-moderate impairment or greater at baseline (see details below); (2) active delirium by medical record review or initial cognitive testing; (3) any hospitalization within 3 months prior to enrollment—to minimize the risk of delirium in previous 3 months; (4) terminal condition (i.e., life expectancy < 6 months), including terminal diagnoses such as metastatic cancer, pancreatic cancer, or receiving palliative care; (5) heavy alcohol history—due to the risk of delirium tremens including documented evidence of alcohol abuse or history of alcohol withdrawal within last 6 months, and greater than 5 drinks per day (for men) or greater than 4 drinks per day (for women); (6) legal blindness and total deafness due to inability to complete neuropsychological testing (lesser degrees of vision/hearing impairment will be included); (7) History of schizophrenia or psychosis; (8) Current chemotherapy;

In the first stage of our dementia screening process, we will exclude all patients with a history of dementia or use of dementia drugs by medical record review or physician report, or with a 3MS score of <69 or its education-adjusted equivalent (correlates with MMSE score \leq 20) on the screening interview (*Tombaugh 1996*). The education-adjusted scores (*Khachaturian 2000*) are \leq 60, \leq 66, \leq 69, \leq 70, \leq 72, \leq 73 for persons with <8, 8-11, 12, 13-15, 16, 17+ years of education, respectively. For the second stage (baseline interview), patients scoring in the abnormal range on any 2 tests (> 1 SD below mean) in the neuropsychological battery will be adjudicated by an expert panel including 2 neurologists, 1 neuropsychologist, 1 geriatric psychiatrist and 2 geriatricians, with review of all study data including interviews, neuropsychological testing results, informant-rated Dementia Questionnaire (DQ, *Silverman 1987*) where available, and medical record data. The expert panel members will review cases quarterly. This 2-stage process should allow us to identify all patients with probable dementia.

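### Project 2 does not separate blood samples drawn before delirium onset from those drawn during or after it, so the POD 2 and one-month contrasts cannot by themselves support a risk-marker reading

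*Protocol*

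**What the plan says.** All references are to the protocol.

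- **Sampling.** A.4.1 collects blood at baseline, then "immediately after surgery in the post-anesthesia care unit (PACU), 3) on postoperative day 2 (POD 2), and 4) one-month after surgery". All four times are fixed without reference to when delirium starts.
- **Groups.** A.4.2 builds a "matched longitudinal biomarker discovery sample of 50 surgical participants with delirium and 50 matched surgical participants without delirium", and later a validation sample grouped in the same way. The resulting signatures are then related to cognitive and functional outcomes up to 18 months.
- **Analysis.** B.1.2 will "examine the relationship of biomarkers to delirium at each of the four time points in the biomarker discovery sample (N=100"). Its power calculation compares mean component level between patients with and without delirium.
- **Roles.** For Project 2 Aims 1 and 2, Table 3 puts delirium under outcome and the cytokine or protein signature under predictor, with conditional logistic regression among the methods. The effect of interest for Aim 1 is "Cytokine profile dif. by delirium".
- **Delirium rating.** Under A.3.2.3.1, "The CAM rating will be completed at baseline, daily during each hospitalization, and at each follow-up assessment". The interviewer rating is "augmented with delirium rated as present by medical record review during the index hospitalization, since delirium can occur between interviews".
- **Purpose.** B1 counts biomarkers among the new risk factors for delirium that the programme wants to understand.

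No section uses onset date to choose, match or classify the Project 2 samples.

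**The concern.** A risk marker has to be measured before the event. A sample drawn during or after delirium can differ because of the delirium itself, its cause or its treatment.

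The plan gives all four samples the same role. At POD 2 the case group can hold patients who will become delirious later, patients who are delirious when sampled and patients whose delirium has already cleared. A case-control difference at that time has no single meaning: it may precede delirium, accompany it, or both. At one month the in-hospital episode is past its onset, so the sample cannot predict that episode.

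Two things are at stake. A marker that rises only after onset could be taken for a risk marker. A marker of active delirium could be weakened by cases not yet delirious when sampled. The signature carried into validation and into the 18-month analyses would inherit the ambiguity.

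**Working it through.** **Step 1. Position of each sample relative to onset**

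| Sample | Relation to onset | Basis |
|---|---|---|
| Baseline | before | C.1.2 excludes "active delirium by medical record review or initial cognitive testing" |
| PACU | very likely before | drawn immediately after surgery |
| POD 2 | before, during or after | delirium is rated daily through the stay; cases are not selected by onset |
| One month | after onset of the in-hospital episode | drawn one month after surgery |

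The problem is therefore confined to POD 2 and one month.

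**Step 2. How the same table treats Project 3.** For H 1.1 to 1.3, delirium incidence is the outcome and the imaging marker the predictor. For H 2.1 to 2.3, change in the marker is the outcome and delirium the predictor. The roles are reversed once the marker is followed past the delirium episode. Project 2 Aims 1 and 2 keep one direction for all four samples.

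**Step 3. Reproduce the plan's figure.** Inputs from B.1.2 and A.4.2: 50 per group, two-sided 5%, two-sample t-test, no within-pair correlation, detectable difference 0.57 SD.

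Noncentrality = d × √(n/2) = 0.57 × √25 = 2.85, with 98 degrees of freedom. Power is 80.6%, and the exact 80% point is 0.566 SD. The 0.57 SD figure reproduces. It treats the 50 cases as one homogeneous group at every time point.

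**Step 4. Illustrate dilution at POD 2.** The share q of cases already delirious at the draw is an assumption, because the documents give no onset times. Assume also that only those cases carry a difference of d = 0.57 SD and the others carry none. The pooled difference is q × d.

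| q | Pooled difference | Noncentrality (× 5) | Pooled power | Active cases, n per group | Noncentrality 0.57√(n/2) | Power, active stratum |
|---|---|---|---|---|---|---|
| 30% | 0.17 SD | 0.855 | about 14% | 15 | 1.56 | about 33% |
| 50% | 0.29 SD | 1.425 | about 29% | 25 | 2.02 | about 51% |
| 70% | 0.40 SD | 1.995 | about 51% | 35 | 2.38 | about 65% |

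Allowing for the extra spread in a mixed case group, with variance 1 + q(1 − q)d², and using a normal approximation, pooled power becomes 13%, 29% and 50%. The picture does not change.

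**Step 5. Vary the effect size.** With a true active-case difference of 1.0 SD and the same allowance for spread, pooled power at q = 30%, 50% and 70% is about 30%, 65% and 92%. Dilution matters much less if effects are large.

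**The case against.** The best defence is that Project 2 claims association, not prediction. B1 speaks of a cytokine signature associated with delirium, Table 3's effect of interest is a difference in profile, and B.1.2 already compares biomarker means by delirium status. In a matched case-control analysis, conditional logistic regression puts case status on the left-hand side by construction, which implies no time order. The time points are examined separately, so a one-month result would carry its own label. Classing samples by onset could also sit in an analysis plan that is not shown, and the daily ratings it needs are being collected.

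Much of this stands. A reader might infer that POD 2 and one-month results will be reported as predictors of delirium; no section says so. A reader might also take delirium at any time in the stay as Project 2's written case definition. That is inferred from A.3.2.3.1 and from the two-week interview in A.3.1.5.1, which is for "patients who had delirium at any time during the index hospitalization"; A.4.2 says only with delirium.

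The dilution figures are open to challenge too. They start at the 80%-power threshold, so any dilution must fall below 80%. They assume no signal before onset, which rules out a true risk marker. B.1.2 also says its detectable effects are well below the differences seen in pilot data.

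What does not fall away is the assignment of roles. Table 3 is more than a generic column heading, since it reverses the roles for Project 3 and not for Project 2, and B1 does speak of risk factors. Even as pure association, the POD 2 contrast mixes states that the data could separate.

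**Conclusion.** The point holds as a limit on interpretation. The POD 2 contrast can mix pre-onset, active and possibly resolved cases, and the one-month sample follows the in-hospital episode, so neither can by itself support a risk-marker claim. Baseline contrasts are not affected, and PACU contrasts very likely are not.

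The size of any dilution at POD 2 cannot be computed from the documents. Pooled power of about 14% to 51% is an illustration that rests on three assumptions: 30% to 70% of cases delirious by the draw, a 0.57 SD difference in those cases, and none in the rest. It should not be read as the actual power of Project 2.

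Nor do the documents support dropping the pooled contrast. It is a legitimate measure of association, and the strata that would replace it are small. This is a cheap improvement that guards against reverse causation; it does not invalidate the design.

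**What to change.** - **Keep** the with/without-delirium contrast at each of the four time points, and describe it as an association.
- **A.4.2:** class each case's POD 2 sample as pre-onset, active or resolved from the daily CAM and the actual draw date. State how cases identified only by chart review are classed, since they may have no CAM onset date. Report the POD 2 contrast by class, each case with its matched control, as a pre-specified secondary analysis.
- **Claims:** limit risk-marker statements to pre-onset samples, that is baseline, PACU, and POD 2 in cases not yet delirious.
- **Table 3:** show one month, and POD 2 in active or resolved cases, with delirium as the grouping variable, as is done for Project 3 H 2.1 to 2.3.

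The cost is analysis-plan wording, with no new blood draws or assays. The downside is precision: at 0.57 SD, active strata of 15 to 35 pairs have only about 33% to 65% power, and the pre-onset strata shrink as the active ones grow. That is why the classification should be added to the pooled contrast and not replace it.

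### The Project 2 best-case detectable difference of 0.26 SD does not follow from 50 matched pairs with r = 0.3; those inputs give about 0.48 SD, and power at 0.26 SD is about 33%, not 80%

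*Protocol*

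**What the plan says.** Section A.4.2 of the protocol defines the Project 2 discovery set as a "matched longitudinal biomarker discovery sample of 50 surgical participants with delirium and 50 matched surgical participants without delirium". Section B.1.2 justifies its size. Biomarker principal components will be related to delirium "at each of the four time points in the biomarker discovery sample (N=100" participants in total).

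On the method, B.1.2 states: "The power estimate is based on the 2-tailed 2-sample t-test". The error rate is two-sided 5%, and the effect is expressed as a fraction of the standard deviation. The section names the correlation of biomarker levels within matched pairs as the other factor that drives power, and sets two values for it: "worst case scenario (no correlation), and best case scenario (moderate correlation, Pearson $r=0.3").

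The result is given as "we can detect 0.57 S.D. unit differences (medium effect) under the worst case scenario and a 0.26 SD unit (small effect) differences", where the second figure belongs to the correlated case and both are said to hold at 80% power. The section then describes these effects as small to medium, says they lie well below the differences seen in pilot data, and concludes that power for biomarker discovery ranges from good to excellent.

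**The concern.** The two detectable differences share the same test, error rate, power and sample, and differ only in the assumed within-pair correlation. A correlation of 0.3 is modest and should bring a modest gain from matching. The printed figures instead show the detectable difference falling by more than half, from 0.57 to 0.26 SD.

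The 0.26 figure is the sole basis for calling any detectable effect small, and it supports the upper end of the power claim. If it is wrong, the protocol credits the discovery step, from which both the cytokine and the protein signatures are carried into validation, with a sensitivity to small differences that it lacks. A reader who relied on 0.26 SD could also take a null discovery result as evidence against small differences.

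**Working it through.** **Inputs, all from the protocol**

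- Two-tailed t-test, Type-I error 0.05, power 80% (B.1.2).
- Discovery sample of 100 (B.1.2), as 50 with delirium and 50 matched without, so 50 pairs (A.4.2).
- Within-pair correlation r = 0 (worst case) and r = 0.3 (best case) (B.1.2).
- Effect in SD units, so SD = 1 (B.1.2).

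**Formulas (exact non-central t)**

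- Unpaired, n per group: df = 2n − 2, noncentrality = d × √(n/2).
- Paired, n pairs: the SD of a within-pair difference is √(2(1 − r)), so df = n − 1 and noncentrality = d × √(n / (2(1 − r))).

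With df = 49, 80% power at two-sided 5% needs a noncentrality of 2.858. The detectable difference is therefore d = 2.858 × √(2(1 − r)/50).

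**Step 1: reproduce the worst case**

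- Unpaired, 50 per group: d = 0.566.
- Paired, r = 0: d = 2.858 × √(2/50) = 2.858 × 0.200 = 0.572.

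Both round to the printed 0.57. The test, error rate, power, sample size and scale (between-person SD) are thus read as the authors used them.

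**Step 2: change only r, to 0.3**

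- SD of the difference: √(2 × 0.7) = 1.18.
- d = 2.858 × √(1.4/50) = 2.858 × 0.1673 = **0.478 SD**.
- Short check: 0.57 × √0.7 = 0.57 × 0.837 = 0.48.

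The printed ratio is 0.26/0.57 = 0.456. Its square, 0.21, would have to equal 1 − r, which implies r near 0.79.

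**Step 3: what 0.26 SD would require**

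| Setting | Result |
|---|---|
| Power at 0.26 SD, 50 pairs, r = 0.3 | 33.1% |
| Correlation needed for 80% power at 0.26 SD, 50 pairs | about 0.79 |
| Pairs needed for 80% power at 0.26 SD, r = 0.3 | 165 |

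**Step 4: other readings, all at r = 0.3 and 80% power unless stated**

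| Reading | Detectable difference |
|---|---|
| One-sided, 50 pairs | 0.42 |
| Two-sided, 100 pairs (discovery and validation combined) | 0.33 |
| One-sided, 100 pairs | 0.30 |
| In units of the SD of the within-pair difference, 50 pairs | 0.40 |
| Mean of the four time points (correlation 0.3 between them), unpaired | 0.39 |
| Mean of the four time points, paired | 0.33 |
| Two-sided, 50 pairs, r = 0.8 instead of 0.3 | 0.256 |

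Only the last row rounds to 0.26, and it contradicts the stated correlation. Whether that is where the figure came from cannot be told from the protocol.

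**The case against.** The strongest reply is that 0.26 SD is openly a best case. The worst case, 0.57 SD, is printed beside it and is correct. If 0.57 SD already lies well below the pilot differences, as the protocol says, the overall conclusion may survive without the smaller figure. Nothing shows that 0.26 SD set the sample at 50 plus 50, and section B.1 describes a process led by the eligible population and feasibility. This bears on how much hangs on the error, but it does not remove it. No pilot effect sizes are given, so the comparison can be neither confirmed nor refuted.

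A second objection is that B.1.2 names a two-sample test and Table 3 lists principal components and conditional logistic regression, so 0.48 SD rests on a paired t-test that is never named. A correlation within matched pairs can only help through a paired analysis, so this is the natural reading, but the corrected text should say so.

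A third is that calling power adequate for medium effects could mislead, because B.1.1 places medium at 0.50 SD. At exactly 0.50 SD, power is 70% unpaired, 69% paired with r = 0, and 83% paired with r = 0.3. That is correct, and it is why the replacement must carry the range 0.48 to 0.57 SD and not the word medium alone. B.1.2 itself calls 0.57 SD a medium effect.

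Lastly, no passage says that a null result will be read as excluding small differences. That remains a risk for readers; it is not something the plan states.

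**Conclusion.** The concern holds. With the protocol's own inputs the best-case detectable difference is 0.48 SD, against the printed 0.26 SD, a factor of 0.478/0.26 = 1.8. At 0.26 SD the design has 33% power, so about two in three true differences of that size would be missed even under the favourable correlation. Combining the discovery and validation samples into 100 pairs gives 0.33 SD, with 59% power at 0.26 SD.

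This rests on a paired t-test on the between-person SD scale, the scale on which 0.57 SD reproduces. The 0.57 figure stands. The small-effect label falls with the 0.26 figure, and the conclusion on power loses the support it drew from it. The statement about pilot data is neither supported nor contradicted here.

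**What to change.** In section B.1.2:

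- Replace the best-case figure and its label with *0.48 SD unit (medium effect)*, and state the basis: paired t-test, 50 pairs, within-pair correlation 0.3, difference in units of the between-person SD.
- Replace the description of the effects as small to medium, and the closing claim about power, with *adequate power for medium effects (0.48–0.57 SD)*. Keep the numeric range in the sentence.
- If a correlation other than 0.3 was actually used, state it and justify it. A value near 0.8 would be needed to keep 0.26 SD, and it could not be called moderate alongside r = 0.3.

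The cost is wording in one section and a less favourable stated figure. Recruitment, matching, blood samples and assays are unchanged.
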